6.2.1.1. Subgroup Analysis

The change from baseline in 6MWD will be summarized by visit for subgroups below for ITT population:

- Region (North and Latin America, Europe, Asia Pacific)
- Stop codon (UAA, UAG, UGA)

In addition, the change from baseline in 6MWD will be summarized at each post-baseline visit for the following subgroups for ITT population:

- Baseline disease severity

- Baseline 6MWD <300 meters
- Baseline 6MWD \geq 300 meters to <400 meters
- Baseline 6MWD \geq 400 meters

6.2.1.2. Time to 10% Persistent Worsening in 6MWD

Time to 10% persistent worsening in 6MWD, defined as last time that 6MWD was not 10% worse than baseline, will be evaluated using a Log-rank test and Kaplan-Meier plot, as well as a Cox proportional hazards model (assuming similar covariates as the primary efficacy model) in ITT populations. For subjects who do not have 10% 6MWD worsening, time to 10% persistent 6MWD worsening will be censored at the time of the last 6MWT during the overall period. For subjects who have all post-baseline assessments more than 10% worse than the baseline, the event will be assigned to Day 1. Subjects who become non-ambulatory will be considered to have 10% worsening at the time of becoming non-ambulatory. The proportion of 10% persistent worsening by Week 144 will also be summarized.

In addition, time to 30 meter drop in 6MWD will also be analyzed in a similar way to time to 10% persistent worsening in 6MWD.

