Every other day	0.75-1.25 mg/kg (recommended)	2 mg/kg (recommended)
High-dose weekend	5 mg/kg given each Friday and Saturday (recommended)	
Intermittent	0.75 mg/kg for 10 days alternating with 10-20 days off medication (recommended)	0.6 mg/kg on days 1-20 and none for the remainder of the month (recommended)

For the daily regimen, 0.3 mg/kg is the minimum acceptable dose but either 0.75 (prednisone/prednisolone) or 0.5 (deflazacort) mg/kg is preferred. For the other regimens, a recommended dose or dose range is provided in the table although no set dose or dose ranges have been clearly accepted as optimum.

Reference: [Bushby 2010a](#)

7. 6MWD \geq 150 meters at screening, baseline Day 1, and baseline Day 2. When Version 3 is implemented or approximately 270 subjects have enrolled in the study, only subjects who meet the mITT criteria, 6MWD \geq 300 meters at Baseline Day 1 or Day 2, and time to stand from supine \geq 5 seconds at Baseline Day 1, will be eligible to enroll. **Note: Personal assistance or use of assistive devices for ambulation (eg, short leg braces, long leg braces, or walkers) will not be permitted during the 6MWT.**
8. Results of the two Baseline 6MWD results must be determined as valid and results of the Day 2 Baseline 6MWD must be within 20% of the Day 1 Baseline 6MWD.
9. Baseline 6MWD (maximum of valid Day 1 and Day 2 values) must be no more than a 20% reduction from the valid Screening 6MWD.
10. Ability to perform timed function tests (run/walk 10 meters, climb 4 stairs, descend 4 stairs, stand from supine) within 30 seconds at screening and baseline.
11. In subjects who are sexually active, willingness to abstain from sexual intercourse or employ a barrier or medical method of contraception during the study drug administration and 4-week follow-up period.
12. Willingness and ability to comply with scheduled visits, drug administration plan, study procedures, laboratory tests, and study restrictions. **Note: Psychological, social, familial, or geographical factors that might preclude adequate study participation (in particular, the ability to satisfactorily perform the 6MWT) should be considered.**

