2.6. Study Assessments

2.6.1. 6-Minute Walk Test

The 6MWT will be performed at Screening (Visit 1), baseline (Visit 2, two 6MWTs performed), Week 12 (Visit 3), Week 24 (Visit 4), Week 36 (Visit 5), Week 48 (Visit 6), Week 60 (Visit 7), and Week 72 (Visit 8, two 6MWTs performed), Week 96 (Visit 9), Week 120 (Visit 10), and Week 144 (Visit 11 - End of Treatment/Premature Discontinuation).

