4.3. Baseline and Endpoint Definitions

Two baselines will be used for open-label data analysis, study baseline and on-ataluren baseline.

The study baseline, defined as the last assessment prior to randomization, will be used for analyzing and summarizing efficacy endpoints. Study baseline 6MWD is defined as the maximum measurement of valid Day 1 and Day 2 6MWD values.

The on-ataluren baseline, defined as the last available measurement prior to the first dose of ataluren, will be used for summarizing safety endpoints.

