All assessments will be assigned to a study analysis visit based on the corresponding study days. For a given subject, if multiple assessments are within the same analysis window, the one closest to the scheduled visit day will be used for that analysis visit. In case of equal number of days to the scheduled visit day, the later assessment will be used for that given analysis visit.

For 6MWD at Visit 8, the date corresponding to the maximum of Day 1 and Day 2 will be used for deriving the study analysis visit.

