6.2.2. Other Secondary Efficacy Variables

6.2.2.1. Time to 10% Persistent Worsening in 6MWD

Time to 10% persistent worsening in 6MWD, defined as last time that 6MWD was not 10% worse than baseline, will be evaluated using a Log-rank test and Kaplan-Meier plot, as well as a Cox proportional hazards model (assuming similar covariates as the primary efficacy model) in both mITT and ITT populations. For subjects who do not have 10% 6MWD worsening, time to 10% persistent 6MWD worsening will be censored at the time of the last 6MWT during the double-blind period. For subjects who have all post-baseline assessments more than 10% worse than the baseline, the event will be assigned to Day 1. Subjects who become non-ambulatory will be considered to have 10% worsening at the time of becoming non-ambulatory. The proportion of 10% persistent worsening by Week 72 will also be summarized.

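### The open-label 10% and 30 m worsening events set single walks against a best-of-two baseline and let one unconfirmed final walk count as persistent

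*SAP*

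**What the plan says.** Open-label SAP 6.2.1.2 dates the event at the last test that was still within 10% of baseline: "Time to 10% persistent worsening in 6MWD, defined as last time that 6MWD was not 10% worse than baseline". The censoring rule covers only boys without the event: "For subjects who do not have 10% 6MWD worsening, time to 10% persistent 6MWD worsening will be censored at the time of the last 6MWT". A second event is defined by analogy: "time to 30 meter drop in 6MWD will also be analyzed in a similar way to time to 10% persistent worsening in 6MWD".

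The reference value comes from open-label SAP 4.3: "Study baseline 6MWD is defined as the maximum measurement of valid Day 1 and Day 2 6MWD values". The visit schedule in 2.6.1 has two walks at only one post-baseline visit: "Week 72 (Visit 8, two 6MWTs performed), Week 96 (Visit 9), Week 120 (Visit 10), and Week 144 (Visit 11". Section 4.9 confirms that the Week 72 value is also a best of two: "For 6MWD at Visit 8, the date corresponding to the maximum of Day 1 and Day 2 will be used".

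Double-blind SAP 6.2.2.1 uses the same 10% rule over 72 weeks and adds: "The proportion of 10% persistent worsening by Week 72 will also be summarized". The later change document for the double-blind analysis (its 3.2.2.1) leaves that analysis unchanged for the ITT population.

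On status, the open-label version history describes the 10% and 30 m analyses as added sensitivity analyses, although 6.2.1.2 sits under the secondary efficacy variables. Open-label SAP 4.7 applies no multiplicity adjustment.

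**The concern.** There are two separate features, and no other section corrects either.

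- **The comparison is not like for like.** The higher of two noisy walks lies above a boy's own mean. A single later walk does not. Part of the 10% or 30 m is used up before any disease change occurs.
- **Persistence is not tested at the end of follow-up.** A mid-study dip that recovers is correctly not an event. A dip at the last test is an event, because nothing follows it. No minimum number of worsened visits is set.

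The protocol's entry rule shows that such dips can occur: "results of the Day 2 Baseline 6MWD must be within 20% of the Day 1 Baseline 6MWD". A boy who walks 400 m and then 340 m is eligible. His second walk is already 15% and 60 m below his own baseline of 400 m.

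What is at stake is the reported proportion worsened by Week 144 and the meaning of the word persistent. The 30 m event has a further gap: its text does not say whether persistence is required.

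**Working it through.** The documents state no false-event rate, event count or power for these endpoints, so there is no figure of theirs to reproduce.

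**Inputs from the documents.** Baseline is the maximum of two walks. Week 72 is the maximum of two. All other post-baseline visits are single walks. The thresholds are 10% and 30 m. Inclusion criteria 8 and 9 apply 20% limits.

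**Assumed inputs.** True distance 360 m; independent normal noise with a CV of 4%, 6% or 8%. The slopes in step 3 are also assumed.

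**Step 1: shift in the reference.** The expected maximum of two independent normal values exceeds their mean by SD/√π = 0.564 SD. At 360 m and CV 6%, the SD is 21.6 m and the shift is 0.564 × 21.6 = 12.2 m, about a third of the 36 m that makes up 10%.

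**Step 2: an exactly stable boy (Monte Carlo).** An event is a last test below 0.9 × reference, or at least 30 m below the reference. Ranges show results with and without inclusion criteria 8 and 9 applied.

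| False events | CV 4% | CV 6% | CV 8% |
|---|---|---|---|
| 10%, Week 144 single vs maximum (as written) | 5.5% | 17.0–17.7% | 25.7–27.5% |
| 10%, Week 144 single vs average | 1.7% | 8.0% | 14.6–14.8% |
| 10%, Week 72 maximum vs maximum | 1.0% | 5.6–6.0% | 10.5–11.9% |
| 30 m, Week 144 single vs maximum | 12% | 25–26% | 33–35% |
| 10%, Weeks 120 and 144 both worse, vs average | 0.1% | 1.4–1.5% | 3.9–4.0% |

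If every boy without a true event were exactly flat, the excess would be (1 − true share) × false rate. With true shares of 30–40%, the as-written excess runs from 0.6 × 5.5% = 3.3 points to 0.7 × 27.5% = 19 points. Against the average it runs from 0.6 × 1.7% = 1.0 to 0.7 × 14.6% = 10 points.

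**Step 3: varied slopes.** Slopes are normal with SD 1.0 m/week and mean −0.25 or −0.6 m/week, with no dropout. Each cell gives the Week 144 share worsened by 10% for the two means.

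| CV | True | As written | Average reference | Confirmed, average reference |
|---|---|---|---|---|
| 4% | 50.0 / 63.7 | 52.0 / 65.5 | 50.0 / 63.6 | 46.5 / 60.1 |
| 6% | 50.0 / 63.6 | 53.0 / 66.2 | 50.0 / 63.4 | 45.3 / 58.9 |
| 8% | 49.9 / 63.7 | 53.8 / 67.0 | 49.9 / 63.3 | 44.0 / 57.7 |

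As written, the overstatement is 1.8 to 3.9 points. The average reference is within 0.4 points of the truth. The confirmed version is 3.5 to 6.0 points too low at Week 144, and 6 to 10 points too low if applied at Week 72. With 180 boys per arm and CV 6%, log-rank power at Week 144 is 79% as written and 78% with confirmation and the average reference.

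**Step 4: the open 30 m definition.** For a stable boy at 350 m with an assumed SD of 20 m, the 30 m false rate is 22.8% if the drop must hold to the last test. It is 67.5% if a first drop at any visit counts. The wording excludes neither reading.

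**The case against.** The strongest case on the other side has four parts.

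1. **Nobody in this trial is exactly flat for 144 weeks.** The ITT population covers the full range of function. Protocol 11.2.3 expects 6MWD to improve up to age 7, and 11.2.4 expects a high risk of losing ambulation below 300 m. With varied slopes, errors around the threshold run in both directions and largely cancel. This stands, and step 3 shows it.
2. **The noise level is unknown.** The 20% entry rule is an outer limit, not a typical spread, and protocol 11.1.2 calls the test accurate and reproducible. This stands for the size of the effect, not for its direction.
3. **A confirmation rule has its own cost.** Open-label visits are 24 weeks apart, so requiring two visits drops any worsening first seen at Week 144 other than loss of ambulation. Censoring a boy at the visit where he worsened is informative. This stands.
4. **Little rests on these endpoints.** The double-blind version is outside the fixed test sequence, and the open-label versions are labelled sensitivity analyses. This stands.

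A reader might infer that noise necessarily pulls the hazard ratio toward 1 and that the definition should be replaced in both SAPs. The documents do not support that. If every non-worsener is flat and the true shares are 30% vs 40%, confirmation with the average reference does raise Week 144 power (38% to 48% at CV 6%). With varied slopes the gain disappears. For the double-blind data, the first lock was on 11 April 2022 and the change document's Table 1 already reports treatment differences, so a new definition there would be chosen after unblinding.

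**Conclusion.** Both features are in the text of open-label SAP 6.2.1.2: a single walk at Weeks 12–60, 96, 120 and 144 is judged against a best-of-two baseline, and one unconfirmed low final walk counts as persistent. For an exactly stable boy the false 10% rate at Week 144 is about 6%, 17% and 26–28% at assumed CVs of 4%, 6% and 8%. For a population with varied slopes the net overstatement of the Week 144 proportion is about 2–4 points. All of these sizes rest on assumed noise, and the last also on assumed slopes.

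Three limits apply. The best-of-two mismatch is absent when Week 72 is the last test, which covers boys who complete the double-blind period; only the missing confirmation remains there. It does apply to a boy whose last double-blind test is a single-walk visit. Noise is the same in both arms, so type I error is not inflated. The study's primary conclusion does not depend on these events.

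The average reference is a clear, cheap improvement. The confirmed-event rule exchanges overcounting for undercounting and is useful only beside the written rule.

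**What to change.** In the open-label SAP, before the final lock:

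1. Derive the 10% and 30 m events against the average of the valid Day 1 and Day 2 baseline walks, with the average at Week 72 as well. Double-blind SAP 6.1.3.5 already uses this average for the 6MWD sensitivity analysis. Report the result beside the maximum-based version.
2. Add, as a sensitivity analysis and not a replacement, a confirmed-event version: two consecutive worsened visits running to the last test, or loss of ambulation. State how an unconfirmed final drop is censored.
3. Write out the 30 m event in full and say whether the drop must persist.

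Leave double-blind SAP 6.2.2.1 unchanged. If these versions are run on the double-blind data, report them only as labelled post-hoc sensitivity analyses.

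The cost is one more derivation and some SAP wording; no new data are needed. The confirmed version will undercount worsening first seen at the last visit and will censor it informatively, and the report should say so.

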6.2.2. Timed Function Tests

A composite score of the average in times to run/walk 10 meters, climb 4 stairs, and descend 4 stairs will be calculated. This calculated composite score, the individual timed function tests, and their corresponding change from baselines will be analyzed during the overall treatment period for ITT population using the similar MMRM categorical model as for 6MWD. The MMRM model will include factors of concomitant corticosteroid type (deflazacort, prednisone/prednisolone) at study baseline, 6MWD category (<300 meters, 300 to <350 meters, 350 to <400 meters, \geq 400 meters) at study baseline, baseline time to stand from supine (<5 seconds, \geq 5 seconds), treatment, visit (analysis visit as a categorical variable), interaction of visit and treatment, interaction of visit and corresponding study baseline TFT score, and corresponding study baseline TFT score.

Subjects who cannot perform a timed function test within 30 seconds, including those who is loss of ambulation (LoA) or the timed function test is above 30 seconds, will be assigned a value of 30 seconds for the respective test for calculating the average change in times. If the average time of the 3 TFT tests is 30 seconds for multiple visits for a subject, the 30 seconds will be kept for the first visit with the assessment of 30 seconds and set to missing for all visits afterwards.

ANCOVA analysis after MI used for 6MWD will also be performed for the composite TFT score and the three individual timed function tests during the overall treatment period for ITT population.

The individual TFT results, and the calculated composite score will be summarized by visit during overall treatment period for ITT population.

The change from baseline in composite average of timed function will be summarized by visit for subgroups below for ITT population:

- Region (North and Latin America, Europe, Asia Pacific)
- Stop codon (UAA, UAG, UGA)

- Baseline disease severity
 - Baseline 6MWD <300 meters
 - Baseline 6MWD \geq 300 meters to <400 meters
 - Baseline 6MWD \geq 400 meters

By-visit summaries on the overall treatment period for the ITT population will also be provided to evaluate the 10-meter run/walk results in subjects with a study baseline 6MWD <300 meters.

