4.8. Missing Data Handling

The analyses using a mixed model repeated measures (MMRM) model will be performed based on available data assuming the missing assessments are missing at random (MAR). As sensitivity analyses, missing assessments for the primary and key secondary endpoints based on the analysis of covariance (ANCOVA) will be imputed using pattern-mixture multiple imputation (MI) as described in Section 6.

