6.2. Secondary Efficacy Variables

6.2.1. Six-Minutes Walking Distance

The average rate of change from baseline in 6MWD over 144-weeks of treatment in the ITT population is considered the key secondary efficacy endpoint of interest for this study in open-label period. The ITT population was specified in the original SAP as a supportive population for the primary endpoint analysis given its importance in providing information on the broad study population (N=359) encompassing the full range of age and ambulatory function. The MMRM category model with a random intercept, baseline 6MWD as a covariate, and factors of baseline concomitant corticosteroid type (deflazacort, prednisone/prednisolone), baseline 6WMD category (<300 meters, 300 to <350 meters, 350 to <400 meters, ≥ 400 meters), baseline time to stand from supine (<5 seconds, ≥ 5 seconds), treatment, visit (analysis visit as a categorical variable), interaction of visit and treatment, interaction of visit and baseline 6MWD, and unstructured covariance matrix (UN), is considered the primary analysis model of interest. In case of non-convergence, other types of covariance matrix are to be used in the order of heterogenous Toeplitz, Toeplitz, and compound symmetric. For this analysis, any subject who lose ambulation during the study was assigned a 6MWD of 0 meters for the first visit in which the subjects lose ambulation and set to 0 meters for all subsequent visits while they participate in the study. The average rate of change in 6MWD over 144-weeks of treatment is calculated from the estimated change from baseline in 6MWD at Week 144 from the MMRM categorical model.

The example SAS code is listed below:

```
PROC MIXED data=<dataset> method=reml;

    CLASS Cortico TTSTBLC Subjid Trt C6WMD AVISIT;
    MODEL CHG6WMD = Cortico C6WMD TTSTBLC Trt B6WMD AVISIT AVISIT*B6WMD
                AVISIT*TRT/S CL;
    RANDOM Int / subject=Subjid;
    REPEATED AVISIT / type= un subject=subjid;
    LSMEANS TRT*AVISIT / pdiff CL;
RUN;
```

where

CHG6WMD = Change from baseline in 6WMD at each visit (Study baseline to Week 144)
B6WMD = Study baseline 6WMD
C6WMD = Study baseline 6WMD category
Cortico = Study baseline concomitant corticosteroid type
TTSTBLC = Time to stand from supine category
AVISIT = Analysis visits as categorical variable
Trt = Treatment group
Subjid = Subject
Int = Intercept

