6.2. Secondary Efficacy Variables

6.2.1. Key Secondary Efficacy Variables

6.2.1.1. *Timed Function Tests - Composite Scores*

The rate of change over 72 weeks (slope) in composite TFT scores will be considered as the first key secondary efficacy endpoint. The composite TFT scores will be defined as the average in times to run/walk 10 meters, climb 4 stairs, and descend 4 stairs. The change in composite TFT scores will be analyzed using the same MMRM model used for the primary analysis with factors of baseline concomitant corticosteroid type (deflazacort, prednisone/prednisolone), baseline 6MWD category (<300 meters, 300 to <350 meters, 350 to <400 meters, \geq 400 meters), treatment, visit, the average time in the three timed function tests at baseline, interaction of visit and treatment, and the interaction of week and baseline average time. The slope will be compared between ataluren and placebo, and the estimated difference in the change at Week 72 will also be provided to facilitate interpretation.

Subjects who cannot perform a timed function test within 30 seconds, including those who is LoA or the timed function test is above 30 seconds, will be assigned a value of 30 seconds for the respective test for calculating the average change in times. Similarly to the primary analysis, if the average time of the 3 TFT tests is 30 seconds for multiple visits for a subject, the 30 seconds will be kept for the first visit with the assessment of 30 seconds, and set for missing for all visits afterwards.

If the test of the primary endpoint is statistically significant, then this key secondary endpoints will be tested at the 0.05 (two-sided) significance level.

As supportive analyses, the same analysis will be repeated:

- ANCOVA based on mITT population after MI
- MMRM model based on ITT population with additional factor of the baseline time to stand from supine (<5 seconds, ≥ 5 seconds) in the model
- ANCOVA based on ITT population after MI (with additional factor of the baseline time to stand from supine (<5 seconds, ≥ 5 seconds) in the model)

The change from baseline in composite average of timed function will be summarized by visit for mITT and ITT populations, and for subgroups below for mITT and ITT populations:

- Region (North and Latin America, Europe, Asia Pacific)
- Stop codon (UAA, UAG, UGA)

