3.2.1.1. Timed Function Tests (TFTs) - Composite Scores

The change in composite timed function tests (TFTs) scores is analyzed using the same MMRM categorical model as used for the primary analysis. Subjects who cannot perform a TFT within 30 seconds, including those who is LoA or the timed function test is above 30 seconds, are assigned a value of 30 seconds for the respective test for calculating the average change in times.

As a supportive analysis, the prespecified ANCOVA model with missing values being imputed using the MI method is also performed.

The change from baseline in composite TFT scores is also summarized by visit for the subgroups specified below in ITT population for both the double-blind and overall treatment periods:

- Region (North and Latin America, Europe, Asia Pacific)
- Stop codon (UAA, UAG, UGA)
- Baseline 6MWD
 - Baseline 6MWD <300 meters
 - Baseline 6MWD \geq 300 meters to <400 meters
 - Baseline 6MWD \geq 400 meters

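### Open-label SAP 6.2.2 deletes repeat 30-second composite TFT values from a visit-wise MMRM read at Week 144, which can materially distort the arm difference

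*SAP*

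**What the plan says.** Open-label SAP (version 2.0), section 6.2.2, averages the 10-meter run/walk, 4-stair climb and 4-stair descend. Boys who cannot do a test in 30 s, including through loss of ambulation, "will be assigned a value of 30 seconds for the respective test for calculating the average change in times". A further rule follows: "If the average time of the 3 TFT tests is 30 seconds for multiple visits for a subject", then "the 30 seconds will be kept for the first visit with the assessment of 30 seconds and set to missing for all visits afterwards". Because each test is capped at 30 s, the average is 30 only when all three are at the cap.

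The composite "will be analyzed during the overall treatment period for ITT population using the similar MMRM categorical model as for 6MWD". Section 4.8 runs such models on available data under missing at random, and section 2.3.2 lists the composite at Week 144 as a secondary endpoint.

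Elsewhere the worst state is handled as follows:

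- **6MWD, open-label SAP 6.2.1:** after loss of ambulation the distance is "set to 0 meters for all subsequent visits while they participate in the study".
- **NSAA, open-label SAP 6.2.3:** an activity lost to progression scores 0 and is expressly not missing.
- **Protocol 9.4.5.1:** 30 s is assigned, with no deletion.
- **Double-blind SAP 6.2.1.1 (slope of the composite):** "the 30 seconds will be kept for the first visit with the assessment of 30 seconds, and set for missing" at later visits, by analogy with the 6MWD slope analysis in its section 6.1.2.
- **Changes from Planned Analysis, 3.2.1.1 (categorical model):** boys who cannot do a test "are assigned a value of 30 seconds for the respective test for calculating the average change in times"; nothing is said on deletion.

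**The concern.** In a straight-line model there is an argument for counting a floor value once, since repeating it bends the line. That argument goes when visit is a category, because each visit has its own mean and the Week 144 mean should include every boy whose Week 144 status is known. Version 2.0 replaced the slope model with the categorical one and carries 0 m forward for 6MWD, but it kept the slope-era sentence for the composite. Section 8, which lists changes from the protocol, does not mention it.

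The values removed are the worst possible ones, at the visit where the endpoint is read and after the longest time for losses to build up. What replaces them is a linear prediction that does not know the scale stops at 30 s.

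**Working it through.** **Plan's own figure.** There is none for this endpoint. The only design calculation (double-blind SAP 2.4, 6MWD slope) reproduces: 2 × (1.960 + 1.036)² × 2.058² / 1.0² = 76.1, so 77 per arm, 154 in all, and 154/0.95 ≈ 162. This point does not depend on it.

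**One boy.** Assume a baseline composite of 6 s and loss of all three tests at Week 96. The change of 30 − 6 = +24 s is kept at Week 96. At Weeks 120 and 144 it is again +24 s by the plan's own assignment, but is deleted. No larger change is possible for him. A model-implied 44.4 s (a simulated average below) would be a change of +38.4 s.

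**One arm.** Let d be the share of an arm whose Week 144 value is deleted and m the mean the model implies for those boys. Ignoring covariate adjustment, the arm mean moves by d(m − 30). The difference, early-start (E) minus delayed-start (D), moves by d_E(m_E − 30) − d_D(m_D − 30). Two simulated cases, using one average m for both arms:

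- Mild gradual decline: d_D = 0.075, d_E = 0.039, m = 44.4. Shift = (0.039 − 0.075) × 14.4 = −0.52 s. The simulated shift was −1.94 − (−1.15) = −0.79 s; a difference in m between arms, which a common value hides, could account for the rest.
- Loss unrelated to function, 25% visit noise: d_D = 0.104, d_E = 0.084, m = 24.6. Shift = (0.084 − 0.104) × (−5.4) = +0.11 s, towards zero. Simulated: −0.41 − (−0.48) = +0.07 s.

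So the direction depends on which arm has more deletions and on whether m lies above or below 30.

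**Simulation.** The set-up was 179 boys per arm (from N = 359 in open-label SAP 6.2.1), the planned visits, an absorbing 30 s cap, and an unstructured MMRM with visit-by-treatment and visit-by-baseline terms; the other stratification covariates were left out. Each trial was fitted with 30 s kept and with the section 6.2.2 rule. Trajectories, noise and loss rates are assumptions. Week 144 differences in seconds (negative favours early-start):

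| Assumed course | 30 s kept | Later values missing | Ratio |
|---|---|---|---|
| Gradual decline, treatment effect | −1.16 | −1.65 | 1.42 |
| | −1.09 | −1.85 | 1.70 |
| | −1.07 | −3.48 | 3.25 |
| | −1.29 | −6.16 | 4.78 |
| | −2.84 | −8.53 | 3.00 |
| Abrupt loss linked to function | −1.25 | −2.20 | 1.76 |
| | −1.08 | −2.81 | 2.60 |
| Unrelated loss, 6% noise | −1.31 | −2.30 | 1.76 |
| | −0.35 | −1.32 | 3.77 |
| | −0.53 | −0.39 | 0.74 |
| Unrelated loss, 15% noise | −0.85 | −1.27 | 1.49 |
| | −1.06 | −1.24 | 1.17 |
| Unrelated loss, 25% noise | −0.48 | −0.41 | 0.85 |
| | −1.19 | −1.13 | 0.95 |
| | −0.62 | −0.66 | 1.06 |

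The 0.74 row is a 0.14 s move beside a standard deviation of 2.78 s for the estimate, so it is weak evidence of shrinkage.

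- **Deleted share:** about 1% to 31% of an arm.
- **Implied values for deleted boys:** 43–57 s on average under gradual decline (all above 30), 50–100 s under abrupt function-linked loss, and 31–33 s and 24–26 s under unrelated loss at 15% and 25% noise.
- **No treatment effect:** both estimates were near 0 in most settings (one high-loss setting gave −0.15 against −1.63, SD 6.7). The standard deviation was about 1.0 to 6.8 times larger under deletion.
- **Early-start doing worse:** its disadvantage grew, in one run from +0.76 to +3.14 s.
- **Multiple imputation on the deleted data:** no cure. Implied values averaged 44–55 s in the gradual and function-linked settings tried. The Appendix 2 template sets a minimum of 0 and no maximum.

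**The case against.** **Deletion is triggered by an observed value, so missing at random holds in the formal sense, and the boy's earlier times and first 30 s still inform the prediction.** True, but no boy at 30 s ever has a later composite in the data. What follows 30 s is therefore pure extrapolation from a normal model, for values that were never missing.

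**The trigger is narrow and the endpoint is not decisive.** This stands. All three tests must be at the cap at more than one visit, and a first 30 s at Week 144 is kept. With 2–6% at the cap by Week 144, the inflation was about 10–32%, or 0.08–0.17 s. Section 6.2.1 makes 6MWD the key open-label endpoint, there is no multiplicity control (4.7), and time-to-loss analyses (6.2.4) and NSAA zeros also capture loss.

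A reader might go further than the documents allow:

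- **That the rule must inflate the benefit of ataluren.** It need not; the table and the reversed case show this.
- **That the changes document dropped the rule.** It is silent. Its section 2.1 says that nothing else in the model was changed, and it spells out the new 6MWD rule but none for the composite.
- **That Week 72 results would therefore differ between reports.** This rests on that silence, and the Week 72 windows and the visits modelled differ anyway.
- **That ANCOVA after imputation inherits the deletion.** Section 6.2.2 does not say. Double-blind SAP 6.1.3.1 and open-label SAP 6.2.1 keep 0 m at all later visits for the 6MWD ANCOVA, which points the other way.
- **That composite and components contradict each other.** The rule is written only for the average; handling of the single tests is a gap in wording.

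**Conclusion.** The rule is wrong as written for a categorical-visit MMRM. It removes assigned worst values at the endpoint visit and puts unbounded extrapolation in their place, against the protocol and the SAP's own handling of 6MWD and NSAA. The origin in the slope model is an inference from the matching wording, but a strong one.

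The Week 144 difference can be materially distorted. With progressive or function-linked decline, the likelier pattern in this disease, it is typically exaggerated in favour of the arm with fewer losses. With noisy data and loss unrelated to function it changes little, and with no effect the main cost is precision. Ratios ran from about 0.85 to 4.8, apart from the imprecise 0.74. All rest on assumed loss rates, so they show what can happen and do not estimate the bias in this trial. Confidence is high on the inconsistency and moderate on direction and size.

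**What to change.** In open-label SAP 6.2.2:

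1. Delete the set-to-missing sentence.
2. State that 30 s is kept at every visit after loss of the task while the boy participates, for the composite and for each of the three tests.
3. State that this holds for both the MMRM data and the input to multiple imputation.
4. Set a maximum of 30 in PROC MI for the timed function tests.

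The cost is one edit and a re-run of these models. The estimated benefit may become smaller.
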